**Table 4 Endpoints, test methods and hypotheses**

	Hypothesis	Test Method	Endpoint	Acceptance Criteria
A	Subjects reduced exertion performing 6MWT compared to previous prosthesis (primary outcome)	BORG scale	Mean difference in BORG score pre and post 6MWT compared to comparator	$H_0: \mu_1 \leq \mu_2$ $H_1: \mu_1 > \mu_2$ $p<0.05$
B	Subjects improved performance in 6MWT compared to previous prosthesis.	6MWT (meters)	Average distance walked in 6MWT compared to comparator	$H_0: \mu_1 \geq \mu_2$ $H_1: \mu_1 < \mu_2$ $p<0.05$
C	Subjects report on average no worse support in sit to stand and stand to sit than with previous prosthesis.	Self-report: PMQ (Questions 9 and 10) Likert scale 0-4	Total score of PMQ questions 9 and 10 compared to comparator	$H_0: \mu_1 \geq \mu_2 +  M_{NI} $ $H_1: \mu_1 < \mu_2 +  M_{NI} $ $ M_{NI}  = 1$ $p<0.05$
D	Subjects perceived safety in hill descent is no worse than with previous prosthesis.	Self-report: Modified PEQ 14F (rate your safety when walking down a steep hill using the prosthesis) Likert Scale 1-10	Average score compared to comparator	$H_0: \mu_1 \geq \mu_2 +  M_{NI} $ $H_1: \mu_1 < \mu_2 +  M_{NI} $ $ M_{NI}  = 1$ $p<0.05$
E	Subjects perceived safety in stair descent is no worse than with previous prosthesis.	Self-report: Modified PEQ 13D (rate your safety when walking downstairs using the prosthesis) Likert Scale 1-10	Average score compared to comparator	$H_0: \mu_1 \geq \mu_2 +  M_{NI} $ $H_1: \mu_1 < \mu_2 +  M_{NI} $ $ M_{NI}  = 1$ $p<0.05$
F	Subjects perceive no speed limitation while walking with the investigational device.	Self-report(yes/no): „Are you satisfied with your walking speed using your prosthesis/test prosthesis?”  Support question: “Do you feel that your walking speed is limited by your prosthesis/test prosthesis?”	Proportion of subjects (p) reporting satisfaction with walking speed on investigational device.	$H_0: p < 80\%$ $H_1: p \geq 80\%$ $p<0.05$

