The LPI can withdraw the participant from the trial at any time. The reasons shall be documented. There are no pre-specified criteria for discontinuation of participants from the trial. The discontinuation of participants in the trial will not result in replacement with new participants. If withdrawal is due to problems related to the investigational device the participant will be asked for permission to follow the status/condition outside the clinical investigation. The follow-up will be individualized.

Subjects will be enrolled at the clinic, the investigational site that they were contacted from.

The total time period required to implement the clinical investigation is expected to be 15-20 weeks. Each individual subject is expected to participate in the clinical investigation for 4-15 weeks. The estimated time needed to include this number (enrolment period) is up to 6 weeks.

At least 15 subjects are required to finish the protocol (3 visits) for statistical data analysis, as specified in chapter 10.2 Sample size calculation.

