### 10.2 Sample size calculation

Power analysis for the estimated required sample size was conducted using G\*Power. See protocol below:

t tests – Means:	Wilcoxon signed-rank test (matched pairs)
Options:	A.R.E. method
Analysis:	A priori: Compute required sample size
Input:	
Tail(s)	= One
Parent distribution	= Normal
Effect size dz	= 0.7084529
$\alpha$ err prob	= 0.05
Power (1- $\beta$ err prob)	= 0.8
Output:	
Noncentrality parameter $\delta$	= 2.6812808
Critical t	= 1.7676466
Df	= 13.3239449
Total sample size	= 15
Actual power	= 0.8150214

It is therefore expected that **at least 15** subjects are required to complete the protocol with a power of **0.8** and significance at **0.05**. Effect size was estimated for the primary endpoint based on a previous in-house study of the RHEO KNEE, a passive microprocessor controlled prosthetic knee.

Given a drop-out rate of **20%**, up to **18** subjects may be recruited.

For pass/fail criteria, see Table 4 **Endpoints, test methods and hypotheses**.

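### Hypothesis F claims no perceived speed limitation, but its endpoint and acceptance rule count only satisfaction with walking speed

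*Combined protocol and SAP*

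**What the plan says.** Table 4, row F, has four parts.

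- **Hypothesis:** subjects perceive "no speed limitation" when walking with the investigational device.
- **Main question (yes/no):** "Are you satisfied with your walking speed using your prosthesis/test prosthesis".
- **Second question, which the row labels as support only:** "Do you feel that your walking speed is limited by your prosthesis/test prosthesis".
- **Endpoint and acceptance:** the share of subjects "reporting satisfaction with walking speed on investigational device", with a null hypothesis below 80%, an alternative of 80% or more, and p < 0.05.

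Sections 10.1 and 10.2 both refer back to Table 4 for the acceptance or pass/fail criteria, so row F is the whole decision rule for this hypothesis. Neither section says how the support question is analysed or what follows if the two answers disagree. Section 10.1 names a paired t-test and the Wilcoxon signed-rank test, and no test for a single proportion.

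**The concern.** Satisfaction and limitation are different judgements. Satisfaction compares walking speed with what the subject expects or wants. Limitation attributes a restriction to the prosthesis. A subject may be content with the speed reached and still feel that the knee caps it. Another may be discontented for reasons unrelated to the knee. The plan asks the two things separately, which suggests that the authors did not regard them as the same.

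Of the two questions, the one that puts the hypothesis to the subject in its own terms is the one with no role in the decision. If the rule is followed as written, the report could declare absence of speed limitation while the subjects' own answers on limitation say otherwise. The opposite can also happen: F could fail because of dissatisfaction although nobody feels limited.

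**Working it through.** **The plan's own figure.** The only computed figure is the sample size for the primary Borg endpoint in section 10.2 ("power of 0.8 and significance at 0.05"), and it does not concern row F. It reproduces. With n = 15, the effective size is 15 × 3/π = 14.324, so df = 13.324. The noncentrality is 0.7084529 × √14.324 = 2.681, the one-sided critical t is 1.768, and the power is 0.815. Row F has no calculation of its own.

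**Inputs.**
- Completers: 15, from section 8.3 ("At least 15 subjects are required to finish the protocol (3 visits) for statistical data analysis").
- Maximum recruited: 18, from section 10.2 ("Given a drop-out rate of 20%, up to 18 subjects may be recruited").
- Threshold 80% and p < 0.05, from row F.
- Assumed, because the plan names no test for a proportion: a one-sided exact binomial test against 0.80, in line with the directional alternative.

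**Step 1: which answers each statement uses.** Cross-classify the n subjects by their two answers:

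| | Not limited | Limited |
|---|---|---|
| Satisfied | a | b |
| Not satisfied | c | d |

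The endpoint in row F is (a + b)/n. The hypothesis in row F concerns (a + c)/n. The two differ by (b − c)/n. They agree for certain only if b = c, and the documents give neither number.

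**Step 2: when the criterion is met.** P(X ≥ x) under p = 0.80:
- 15/15: 0.8^15 = 0.035, met.
- 14/15: 15 × 0.2 × 0.8^14 + 0.8^15 = 0.132 + 0.035 = 0.167, not met.
- 18/18: 0.8^18 = 0.018, met.
- 17/18: 18 × 0.2 × 0.8^17 + 0.8^18 = 0.081 + 0.018 = 0.099, not met.

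Under this test, acceptance needs every subject to be satisfied, at 15 or at 18.

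**Step 3: what acceptance says about limitation.** If all 15 are satisfied, then c = d = 0 and the number not limited is 15 − b, where b may be anything from 0 to 15. Applying the same test and threshold to the limitation answers, for assumed values of b:

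| Satisfied but limited (b) | Satisfaction result | Not limited | p for not limited |
|---|---|---|---|
| 0 | 15/15, met | 15/15 | 0.035, met |
| 1 | 15/15, met | 14/15 | 0.167, not met |
| 3 | 15/15, met | 12/15 | 0.648, not met |

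**Step 4: the other direction.** If nobody feels limited and one subject is dissatisfied for another reason (c = 1, b = 0), satisfaction is 14/15 (p = 0.167, not met), while the proportion not limited is 15/15 (p = 0.035).

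The outcome for F can therefore depend on which question is counted. The values of b and c are illustrations, not estimates.

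**The case against.** The strongest reply is that F is consistent in operation. Main question, endpoint and threshold all concern satisfaction and are fixed in advance; only the hypothesis label differs. Any reader of Table 4 can see what is counted, and no choice is left for after the data are seen. This stands as far as it goes, but the label is the claim that the test is meant to decide.

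Second, the limitation answer is collected, and section 10.3 says in general terms that nothing will be left out of the analysis. The noise row has a similar layout, with a support question beside a proportion endpoint. So a reader should not infer that the limitation answers would be discarded or hidden; the documents do not show that. But the general sentence in section 10.3 gives no rule for disagreement. In the noise row the support question asks about a consequence (preference), not about the claim itself.

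Third, a misleading acceptance is a narrow event under the assumed test, since it needs unanimous satisfaction together with some reported limitation. That is correct, and nothing in the documents suggests how common such disagreement would be.

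Fourth, the 80% threshold was set for satisfaction, and the documents give no basis for carrying it over to the limitation question. This also stands and affects the choice of fix.

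Finally, the contents list a walking-speed item in Appendix 2, but its text is not in the material available here, so a scoring rule there could not be checked.

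**Conclusion.** Row F is wrong as written: it states one construct and decides on another. Meeting its criterion would support satisfaction with walking speed on the investigational device, and would not by itself support absence of perceived limitation. This conclusion rests on the wording of the row alone and does not depend on the choice of test.

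The size is unknown, because the overlap of the two answers is not given. The figure p = 0.035 at 15/15 rests on the assumed one-sided exact binomial test and is not a result that the plan states.

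A reader might infer that the trial is likely to accept a false claim, or that many subjects will feel limited. The documents support neither; they show only that the rule does not guard against it. Nor is the main result affected: F is a secondary hypothesis, and the primary conclusion rests on the Borg comparison in row A.

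**What to change.** Preferred: reword hypothesis F, and the conclusion to be drawn from it, to say that subjects are satisfied with their walking speed on the investigational device. Keep the present endpoint and threshold. State that the limitation answers will be reported beside it as a two-by-two table, including the number satisfied but limited.

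Alternative, if the claim about limitation is to be kept: make the proportion answering no to the limitation question the endpoint, keep satisfaction as the support item, and confirm with a reason that 80% is the right threshold for that question.

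In either case, name the test for a single proportion. The cost is one row of Table 4 and a sentence in section 10.1. Both questions are already asked, so no visit, item or subject is added. The change should be made before the data are seen.

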**For all hypothesis:**

$\mu_1$  is average of measurements with comparator at 2 weeks;

$\mu_2$  is the average of measurements at 2 week follow up (investigational device);

$\mu_3$  is the average of measurements at 8 – 12 week follow up (investigational device);

and  $|M_{NI}|$  is the margin of non – inferiority

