L	The investigational device provides ease of use of gait functions no worse than previous device	Self-report: PMQ (Questions 1 and 3-6) Likert scale 0-4  Objective measure L-test	Total score of PMQ questions 1, 3-6.  Proportion of subjects (p) successfully completing the L-test using gait functions.	For PMQ score: $H_0: \mu_1 \geq \mu_2 +  M_{NI} $ $H_1: \mu_1 < \mu_2 +  M_{NI} $ $ M_{NI}  = 2,5$ $p < 0.05$  For L-test: $H_0: p < 80\%$ $H_1: p \geq 80\%$ $p < 0.05$
M	Side effects N/A	Side effects	Occurrence of side effects	N/A

N	Mobility using the investigational device is no worse than with the comparator	PMQ total score (0-48)	Average total score of the PMQ	$H_0: \mu_1 \geq \mu_2 +  M_{NI} $ $H_1: \mu_1 < \mu_2 +  M_{NI} $ $ M_{NI}  = 5,5$ $p < 0.05$
O	Activity level increases with longer adaptation period on the investigational device	Activity reports from the knee (daily steps, use time)	Activity level after 8-12w follow up compared to 2w follow up on investigational device	$H_0: \mu_2 \geq \mu_3$ $H_1: \mu_2 < \mu_3$ $p < 0.05$

Informative endpoint: In house usability questionnaire (Perceived weight, size, look, ergonomics, fit w/clothes, battery life, preference, falls questionnaire)

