#### Visit 2:

During the second visit subjects in Group 1 will perform the same functional tests as in the first visit (**6MWT, L-test, Borg scale**) on the investigational device and answer questionnaires on the performance of the investigational device, and then be fitted back to their prescribed prosthesis. Subjects in Group 2 will perform the tests/questionnaires on their prescribed prosthesis and then be fitted with the investigational device. A new appointment is made after approximately 2-3 weeks.

CPO subjects will provide feedback on the ease of setup and fitting.

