#### Visit 3:

During the third visit all subject will repeat the tests and questionnaires on the prosthesis they are fitted with. Subjects will have the option to use the investigational device for an additional 8-12 weeks, those who choose that will be fitted with the investigational device or stay on it, depending on which they are fitted with. They will be given an appointment for the fourth visit 8-12 weeks later. They will be contacted via telephone 4-5 weeks later and asked to provide feedback on their experience with the device so far, see script in **Appendix 18.1**. Those that choose not to keep using the investigational device will be fitted back on their prescribed prosthesis and end their participation in the study at visit 3.

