**iii) Measurements and data collection**

The same questionnaires, consisting of four valid instruments (PMQ, PEQ, PLUS-M, Borg) and in-house questions on the performance of the investigational device, will be used and filled in at three-four separate points in time. The same functional tests (L-test and 6MWT) will also be carried out at two points in time (except for those that elect the optional 8-12 week follow up period, there will be an addition visit with data collection and a follow up phone interview), the AMPRO will be performed at baseline to verify users K-level. The activity report will be generated from the Investigational device software application. See Table 6 for visit schedule and study procedures. **Table 6 Visit schedule and procedures**

Procedure/activity	Recruitment phase: 2-6 weeks prior to baseline	Group 1 visit 1: Baseline	Group 2 visit 1: Baseline	Group 1 visit 2: 2/3w F/U	Group 2 visit 2: 2/3w F/U	Group 1 visit 3: 4/6w F/U	Group 2 visit 3: 4/6w F/U	Visit 4 Optional 8-12w F/U
Potential subjects identified, fitting inclusion/exclusion criteria, by PI from customer database	X							
PI calls potential subjects and pre-screens by telephone	X							
Subject signs ICF, randomization		X	X					
Fitting, Training		X			X			
Subject fills in questionnaires		X		X	X	X	X	X
Subject performs 6MWT w/Borg scale and L-test		X		X	X	X	X	X
PI prints out activity report from investigational device				X			X	X
Subjects that choose to keep using the investigational device are given an appointment in 8-12 weeks from visit 3. Others are fitted with their prescribed prosthesis and end participation.						X	X	

All subjects still active are fitted back to their prescribed prosthesis, end of study.	X
CPO subjects provide feedback on fitting the investigational device	X

For each subject there are three scheduled visits to the study site and questionnaires/tasks/measurements administrated three times during the course of the study, with an additional 4th visit which is optional.

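### Hypothesis O attributes a rise in activity to longer adaptation, but the data are an uncontrolled before-after change among subjects who chose to continue, pooling interrupted and continuous use

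*Combined protocol and SAP*

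**What the plan says.** Row O of Table 4 (section 7) states that activity "increases with longer adaptation period on the investigational device". Its endpoint is "Activity level after 8-12w follow up compared to 2w follow up on investigational device", measured as daily steps and use time from the knee's own log. The null is μ2 ≥ μ3 and the alternative μ2 < μ3, with p<0.05 as the acceptance criterion. It is the only row of Table 4 that uses μ3, so it is the only formal test of the long-term part of the objective.

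The visit descriptions in section 8.4 ii determine who supplies the data:

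- At Visit 2, Group 1 is tested on the investigational knee "and then be fitted back to their prescribed prosthesis". Its next visit is about 2-3 weeks later. Group 2 is fitted with the investigational knee at Visit 2.
- At Visit 3, "Subjects will have the option to use the investigational device for an additional 8-12 weeks". Group 1 subjects who accept are fitted with it again; Group 2 subjects who accept simply stay on it.
- "Those that choose not to keep using the investigational device will be fitted back on their prescribed prosthesis and end their participation" at Visit 3.

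In Table 6 the line "PI prints out activity report from investigational device" is marked at Group 1 Visit 2, Group 2 Visit 3 and Visit 4. No activity measure is named for the prescribed knee. Section 10.1 plans a two-tailed paired t-test or Wilcoxon signed-rank test and rules out subgroup analysis. Section 10.3 compares dropouts with subjects who finished the protocol, and section 8.3 defines finishing as three visits.

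**The concern.** O names a cause, and its acceptance criterion is met by any rise. A rise between the two readings could come from adaptation, from the passage of time, or from who remained. The plan has nothing that separates these:

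- Everyone in the extension wears the investigational knee, and subjects who decline leave the study, so no parallel series shows what activity would have done anyway.
- Subjects who decline have finished three visits. They are not dropouts under section 10.3, and no planned analysis describes them.
- Group 1's device use is broken and Group 2's is not, yet the row pools them. The section 10.1 remark on carryover comes with no method that would help here.

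If O passes, the plan as written leads to a stated adaptation effect that the data cannot establish.

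**Working it through.** **The plan's own figure.** No sample size or power is given for O. The calculation in section 10.2 is for the Borg endpoint and reproduces: effective n = 15 × 3/π = 14.32, df = 13.32, δ = 0.7084529 × √14.32 = 2.681, one-sided critical t = 1.768, power 0.815. The 15 are completers of three visits, so the figure says nothing about Visit 4.

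**Timeline, from the stated visit intervals.**

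| | Group 1 | Group 2 |
|---|---|---|
| On-device reading for μ2 | Visit 2 | Visit 3 |
| Gap off the device before the extension | 2-3 weeks | none |
| μ2 reading to Visit 4 | (2-3) + (8-12) = 10-15 weeks | 8-12 weeks |
| Total weeks on the device at Visit 4 | (2-3) + (8-12) = 10-15 | (2-3) + (8-12) = 10-15 |

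Total exposure at Visit 4 is the same in both groups. What differs is continuity and the calendar time between readings.

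**Time trend (main problem).** Assume no adaptation effect, a choice to continue that is unrelated to change, and a drift of d standard deviations of the paired change from season or routine. The test statistic is then noncentral t with n − 1 df and noncentrality d√n. The documents give neither d nor the number continuing. With 15 subjects and about half continuing, simulation gives one-sided rejection at 0.05 of 5% at d = 0, and 18%, 34% and 52% at d = 0.3, 0.5 and 0.7. The formula at n = 7 and n = 8 brackets these: 17-19%, 32-36% and 50-56%. Under the two-tailed test of section 10.1, rejection in favour of O is 10-11%, 20-23% and 35-40%, against a nominal 2.5%.

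**Self-selection.** O is paired, so a subject who likes the knee and is more active at both readings does not bias the change. Bias needs a correlation r between opting in and the subject's own later change. If the most favourable fraction f continues, the mean change is approximately r·φ(z)/f SD, where z is the normal cut-off for f:

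- f = 1/2: φ(z)/f = 0.798, so r = 0.2-0.5 gives 0.16-0.40 SD.
- f = 2/3: φ(z)/f = 0.545, so r = 0.2-0.5 gives 0.11-0.27 SD.

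Simulated for 18 subjects who all reach Visit 3, with no true mean change and no drift:

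| Continuing | r | Favours O, one-sided (nominal 5%) | Favours O, two-tailed test (nominal 2.5%) |
|---|---|---|---|
| 9 | 0.2 | 11% | 6% |
| 9 | 0.5 | 31% | 20% |
| 9 | −0.2 | 2% | 1% |
| 12 | 0.2 | 10% | 5% |
| 12 | 0.5 | 24% | 15% |
| 12 | −0.2 | 2% | 1% |

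Both columns are shown because Table 4 and section 10.2 are one-directional while section 10.1 is two-tailed. The values of r, f and n are assumptions; the documents give none of them.

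**The case against.** Several points on the other side are sound.

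- Because continuers supply both readings, a reader might infer that enthusiasm for the device by itself inflates O. The documents do not support that. The sign of r is unknown, and if subjects with unusually high early activity opt in, regression to the mean would lower the later reading. A negative r gives less than the nominal rate.
- A reader might infer that Group 1's break helps O pass. Both groups reach 10-15 weeks of use, and an interruption could as easily work against O. The break makes the pooled quantity hard to interpret; it does not show a false pass.
- A reader might infer that the Visit 4 report for Group 2 includes the weeks already counted in μ2. No section says the report is cumulative. Overlap would dilute a real change, and Table 6 already schedules a Group 2 reading at Visit 3 from which the extension could be isolated. This is a reason to define the averaging period and does not support a false pass.
- The endpoint column of row O already reads as a plain time comparison, and O is one secondary row.

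What remains is the hypothesis itself, which states a cause, and the absence of any control for time. Pairing does not remove a time trend.

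**Conclusion.** The concern holds for attribution. The planned test can show that activity among continuers was higher at Visit 4 than after the first 2-3 weeks. It cannot show that longer adaptation was the reason, nor that the rise applies to everyone enrolled. The missing control for time is the main weakness: an assumed drift of 0.3-0.7 SD gives an 18-52% chance of a pass without adaptation (one-sided, about half of 15 continuing). Self-selection certainly narrows the population. Whether it also biases the change is unknown. Under assumed correlations of 0.2-0.5, support for O without a true change is about 10-31% one-sided, or 5-20% under the two-tailed test. These figures illustrate sensitivity and are not estimates for this trial. The primary Borg comparison does not use the extension and is unaffected. The change is worth making before analysis because O is the only formal long-term hypothesis.

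**What to change.** 1. Restate O and its conclusion as: *among subjects who chose to continue, activity at 8-12 weeks versus 2 weeks on the device*, with no attribution to adaptation.
2. Report how many continued, and the Visit 2 and Visit 3 results of continuers and decliners, by group.
3. Show O descriptively for Group 1 (interrupted) and Group 2 (continuous). With 9 continuers this would be about 4-5 per group, so no test by group. Add a line to section 10.1 that this display is not a subgroup analysis.
4. Define μ2 and μ3 as daily averages over non-overlapping periods: first fitting to the end of the first 2-3 weeks, and Visit 3 to Visit 4. The reports already marked in Table 6 (Group 1 Visit 2, Group 2 Visit 3, Visit 4) supply most of this. The one addition is a start reading when a Group 1 subject is fitted again at Visit 3.

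The cost is some rewording, a small table and one extra log reading at an existing visit. The downside is a narrower claim for O. An adaptation claim would need a concurrent control for time, which this design does not have.
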